4 STUDY DESIGN

The study will be designed as a prospective surveillance of the immune response to seasonal vaccination in healthy children of varying ages. A schematic of the study design is shown below:

- **Cohort 1A and 1B: Children between 3 and 12 months of age (6 months of age or greater required for participation in the vaccination cohort 1A)**

- **Cohort 2A and 2B: Greater than 12 months of age, birth date after 2009 (early exposure to pH1N1)**
 - Cohort 2A will enroll 35 children <3 years of age and 25 children >=3 years of age
- **Cohort 3A and 3B: Birth date between 2006 and 2009**
- **Cohort 4A and 4B: Birth date between 2003 and 2006 (early exposure to previous seasonal H1N1 strains)**

5 STUDY POPULATION

It is anticipated that this study will enroll a total of approximately 220 subjects. This includes 140 children in the vaccination cohort [20 children between 6-12 months, 60 children with a birth date after 2009 (35 children <3 years of age and 25 children \geq 3 years of age), 30 children with a birth date between 2006 and 2009, and 30 children with a birth date between 2003 and 2006]. We also will enroll up to 80 children total who present with acute influenza infection (20 children into each of the 4 age cohorts). We anticipate having to screen up to 500 children presenting with signs of ILI during the height of seasonal influenza circulation in order to identify and recruit these 80 children with natural influenza infection, as only a small number of children with symptoms possibly consistent with influenza will actually have respiratory infections as a result of influenza virus infection. It is anticipated approximately two-thirds of the children in all cohorts (both A and B) will enroll in the optional year of longitudinal follow-up.

The goal of this study is to understand the development of influenza-specific immunity in a population of children in the Rochester, NY area. Children will be excluded from participation in the study if they meet exclusion criteria of the protocol such as having a documented immunodeficiency or are on immunosuppressive medications expected to have a more than a minimal impact on the development of an immune response to vaccination or infection. Other conditions that may possibly have more than a minimal effect a child's immune system, such as allergies or other hypersensitivity syndromes, mild asthma, or obesity, will be able to enroll in the study. The presence or absence of concomitant medications and medical conditions will be documented and the effect of potential confounding variables will be examined in data analysis.

Children in the vaccination cohort will be recruited either by flyer, via a letter sent under authorship of his/her PCP, or in person at the Strong Pediatric Practice, Elmwood Pediatrics, or Lewis Pediatrics. Children recruited by letter may receive a follow-up phone call from study staff in 1 to 2 weeks to assess interest in participating when possible. We will also reach out to parents/LARs participating in RSRB protocol 58437 and 55570 who have consented for contact regarding future research studies to determine if the subject and parent/LAR are interested in study participation.

Acute influenza cases will be identified through the Strong Pediatric Practice, Elmwood Pediatrics, Lewis Pediatrics, the Pediatric Emergency Departments at Strong Memorial Hospital or Rochester Regional Health, or one of the UR-affiliated Urgent Care Centers by screening patients for ILI. Additionally, we will have flyers with contact information for subjects to call if they have a child with symptoms of ILI. Finally, records from influenza tests performed in the URMIC Clinical Microbiology Laboratory will be reviewed and potentially eligible subjects with a documented acute influenza infection will be contacted to assess for study interest. Please see URMIC Notice of Privacy Practices page 2 section on RESEARCH, which states "*We may use and disclose medical information about you for research purposes. In most cases we will ask for your written authorization. However, under some circumstances we may use and disclose your health information without your written authorization if doing so poses minimal risk to your privacy. We may also release your medical information without your written*

authorization to people who are preparing a research project, so long as any information identifying you does not leave our facility. The researchers may use this information to contact you to ask if you want to participate in such research." Subjects who present with an ILI will complete a brief consent for screening by rapid influenza test and future contact if influenza testing was not completed by the clinical microbiology lab. In the event that influenza testing is pending or has been completed by a medical provider, results of this test will be obtained through review of the medical record. If positive, parents/LARs will be approached to participate in the full study. If rapid influenza testing is negative, a confirmatory PCR will be completed. Children with ILI that initially test positive by PCR performed by the clinical microbiology lab or test negative for influenza by rapid testing but later test positive by PCR will be contacted to determine if there is interest in full study participation. Every attempt will be made to have these children complete all study visits, but in the situation when the parent/LAR is unable to be reached prior to day 5 of illness onset, study visit 1 may be bypassed with enrollment completed at the time of study visit 2.

If funding is available, subjects will have the option to enroll for a additional 1 year follow-up upon reviewing and signing a "consent for longitudinal follow-up" to be presented to the subject and their parent/LAR at one of the scheduled year 2 follow up visits. If subjects sign this consent form and continues to meet all inclusion and exclusion criteria, they will be enrolled and followed under the same subject number, with an "R" appended at the end of the subject number so that they can be identified as a reenrollment.

5.1 Inclusion Criteria

- Age
 - Between 6 and 12 months at the time of enrollment to participate in the vaccination arm of age cohort 1A
 - Between 3 and 12 months at the time of enrollment to participate in the natural infection arm of age cohort 1B
 - > 12 months, birth date after 2009 for either the vaccination (A) or natural infection (B) arm of age cohort 2
 - Birth date between 2006 and 2009 for either the vaccination (A) or natural infection (B) arm of age cohort 3
 - Birth date between 2003 and 2006 for the vaccination (A) or natural infection (B) arm of age cohort 4
- Gestational age of ≥ 37 weeks at birth
- Parent/LAR can provide informed consent, with children ≥ 8 years of age providing informed assent
- Available for the duration of the study
- History of previous primary IIV vaccination (at least 2 previous doses for age <9 yrs, at least 1 previous dose for age 9 and older) **ONLY** for participation in the vaccination (A) arm of age cohorts 2, 3, or 4

- Acute illness documented by rapid influenza test, PCR testing, or testing done by either URM Labs or RGH Clinical Microbiology Labs to be due to influenza virus **ONLY** for participation in the natural infection arms (B) of age cohorts 1-4
- Children enrolled in the Cohort A (vaccination cohort) are required to have an appropriate weight and vital signs as determined by a licensed medical provider. Children enrolled in the Cohort B (natural infection cohort) are required to have an appropriate weight and clinically stable vital signs as determined by a licensed medical provider.
 - Children will not qualify for study participation if their weight is more than 2.5 standard deviations below population norms. This will be determined through calculation of a Z score using the PediTools website (<https://www.peditools.org/>) utilizing the appropriate CDC growth calculators for age [32].

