The age range of the first cohort was chosen to enroll infants in their first influenza season with no history of prior exposure to influenza virus. Thus, this age cohort will allow examination of the true primary response to influenza infection or inactivated vaccination. Children between 6 and 12 months of age who have not previously had an influenza infection or vaccination will be eligible to participate in vaccination cohort 1A. During Visit 1, they will have an initial prevaccination blood draw and will then receive a dose of inactivated influenza vaccine. These children will then receive a booster dose of the inactivated influenza vaccine, with vaccine doses separated by 28 (+ 14) days as recommended by the AAP. A post vaccination blood draw will only be performed following the second vaccine dose [1]. To minimize blood draws, we will perform the next blood draw to interrogate the immune response following the second vaccine dose. Children between 3 and 12 months of age who present with an influenza-like illness will be eligible to participate in the infection cohort (1B). Study personnel will obtain nasal swabs from potential subjects for a rapid influenza antigen test on illness presentation (typically this occurs at day 2-4 post illness onset) if influenza testing was not completed by the clinical microbiology lab. In the event that influenza testing result is pending or completed by a medical provider, results of this test will be obtained through review of the medical record. If positive, subjects will be eligible for further study participation. Given the low sensitivity of rapid influenza testing, influenza real-time RT-PCR will be used to confirm all rapid antigen test results, with subjects recruited for further study participation if RT-PCR testing is positive. In addition, if the subject is eligible for enrollment based on a positive influenza test result by the clinical microbiology laboratory and symptomatic at the time of presentation, a nasal swab for additional influenza real time RT-PCR testing may be obtained during the first study visit (study visit 1, or visit 2 if visit 1 is bypassed) in order to obtain further information regarding the infecting influenza serotype if possible.

The age ranges of the subsequent cohorts were chosen to capture the likely exposure histories of enrolled children, specifically surrounding exposure to the 2009 pandemic H1N1 virus. All of

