Visit 4 (Season 2 day 0): Subjects will be asked to return to the VRU the following fall to receive seasonal influenza vaccination. At this time, the ICF, study requirements and any AE or other illnesses will be reviewed. Subjects will have an interval medical history obtained, including vaccinations and a review of all medications. Any illness memory aids returned will be reviewed to determine if the parent/LAR recorded any symptoms consistent with influenza-like illness that were not reported to study personnel. Subject weight and vital signs will then be obtained and a targeted physical exam performed as indicated by medical history. Following this a sample of peripheral venous blood will be obtained if able. Subjects will then be vaccinated with seasonal IIV. Parents/LARs will use the memory aids to document the symptoms of any illnesses that occur and will be instructed to call the study coordinator if symptoms consistent with an influenza-like illness are present.

Visit 4.5: Vaccine booster visit (Season 2 day 28 +14 days):

Children <9 years of age acutely infected with influenza (cohort B) who have not appropriately received 2 or more total doses of influenza vaccine will present to the VRU to receive their influenza vaccine booster dose on day 28 (+14) following the initial influenza vaccination (Visit 4). At this time, ICF, study requirements, any returned illness memory aids, and any adverse events or other illnesses will be reviewed. An interim medical history, including vaccinations, will be obtained and medications reviewed. A targeted PE will be completed and vital signs and weight obtained. Then a dose of seasonal IIV will be administered intramuscularly.

Visit 5 (Season 2 day 8/36 + 2 days): Subjects may return to the VRU or have a home visit completed on day 8 (+2) following IIV administration (this will be about day 36 following the initial vaccination for children requiring 2 doses of influenza vaccine). At this time, the ICF, study requirements, any returned illness memory aids that document recent symptoms of illness and any adverse events or other illnesses will be reviewed. An interim medical history, including vaccines, will be obtained and medications reviewed. Vital signs and subject's weight will be obtained and a targeted PE performed. Following this a sample of peripheral venous blood will be obtained if able.

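### The 6-12 month age band does not secure the first influenza season that section 2.2 claims for cohort 1A, and the shortfall probably differs between 1A and 1B

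*Combined protocol and SAP*

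**What the plan says.** Section 2.2 gives the purpose of cohort 1. Its age range was "chosen to enroll infants in their first influenza season with no history of prior exposure to influenza virus", and therefore "this age cohort will allow examination of the true primary response to influenza infection or inactivated vaccination". For the vaccinated infants it adds a history condition: "Children between 6 and 12 months of age who have not previously had an influenza infection or vaccination will be eligible to participate".

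Section 5.1 turns this into age at enrolment only: "Between 6 and 12 months at the time of enrollment to participate in the vaccination arm of age cohort 1A" for 1A and "Between 3 and 12 months at the time of enrollment to participate in the natural infection arm of age cohort 1B" for 1B. Cohorts 2 to 4 are bounded by birth date; cohort 1 has no such bound. Neither 5.1 nor 5.2 repeats the history condition from 2.2. For arm A, 5.2 excludes influenza vaccine already given in the current season and does not mention earlier infection.

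On timing, section 5 places the screening for infected children among those "presenting with signs of ILI during the height of seasonal influenza circulation". Section 9.1 places vaccination in the vaccine season without naming months. Fall is named only for later seasons: at Visit 4 subjects are "asked to return to the VRU the following fall to receive seasonal influenza vaccination", and the optional third-season visit is worded alike.

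**The concern.** Whether an infant is in a first season depends on birth date relative to the previous season. Age at enrolment fixes this only once the enrolment date is known, and the two arms of cohort 1 probably enrol at different times of year. A 6-12 month old vaccinated in mid-October was born between mid-October and mid-April, which spans the previous winter. A 3-12 month old infected in mid-February was born between mid-February and mid-November, mostly after that winter.

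Section 11.4 compares children by exposure at each time point, and section 2.2 relies on cohort 1 for priming by infection versus vaccine. If some 1A infants had an unrecognised infection the winter before, their vaccine response is a recall response. With 20 infants per arm, a few such infants concentrated in one arm would matter for a claim about the primary response. The section 11.4 models list age as a covariate, but age does not stand in for season history: the same age implies a different history in October and in February.

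**Working it through.** The documents state no figure to reproduce; section 11.2 declines to estimate precision. The check is birth-date arithmetic.

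**Inputs from the documents:** age 6-12 months (1A) and 3-12 months (1B), section 5.1; 20 infants in each, section 5.

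**Assumptions, not in the documents:** ages uniform within the band; first 1A dose mid-September to mid-December; 1B infection mid-December to mid-March; previous season 1 December to 31 March, or running on to 30 April.

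**Formula.** The oldest eligible infant was born 12 months before enrolment. The share alive during part of the previous season is the number of months from that birth date to the season's end, divided by the width of the band (6 months for 1A, 9 for 1B), capped at 100%.

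- 1A, mid-October dose: mid-October to 31 March is 5.5 months; 5.5/6 = 92%.
- 1B, mid-February infection: mid-February to 31 March is 1.5 months; 1.5/9 = 17%.

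| Season end | 1A: mid-Sep / Oct / Nov / Dec | 1B: mid-Dec / Jan / Feb / Mar |
|---|---|---|
| 31 March | 100 / 92 / 75 / 58% | 39 / 28 / 17 / 6% |
| 30 April | 100 / 100 / 92 / 75% | 50 / 39 / 28 / 17% |

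A count by calendar day differs by about a percentage point.

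**Other season windows.** The table averages 1A doses over 15 September to 30 November and 1B infections over December to March.

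| Window | 1A | 1B | Gap (points) |
|---|---|---|---|
| October-May | 100% | 44% | 56 |
| November-April | 97% | 33% | 64 |
| December-March | 87% | 22% | 65 |
| January-February | 71% | 13% | 58 |

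The 1A share falls to 50% only if dosing slips to about 1 March, 1 February, 1 January and 1 December respectively. The 1B result is less stable: for infection on 1 December it is 67% under October-May and 56% under November-April.

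**Depth of overlap.** Being alive for part of a season can mean one day. For a 15 October dose, the share of 1A infants who lived through the whole previous season is 0%, 8%, 25% and 42% under the four windows. Under December-March, the mean fraction of the previous season lived through is (1.5 × 1 + 4 × 0.5)/6 = 58% for 1A dosed in mid-October. For 1B infected in mid-February it is (1.5 × 0.1875)/9 = 3%.

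**Cost of adjusting for the flag.** With equal arms and shares p1 and p2, the correlation of flag with arm is r = 0.5(p1 − p2)/√(p̄(1 − p̄)), and the standard error of the arm effect grows by 1/√(1 − r²).

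- 0.58 v 0.28 (mid-December, mid-January): r = 0.30, factor 1.05.
- 0.92 v 0.16 (mid-October, mid-February, day count): r = 0.76, factor 1.55.

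The inflation is thus about 5-55% for these pairings; the extreme pairings of the grid fall outside that range.

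**The case against.** The strongest reply is that the protocol already has a check. 1A infants have a pre-vaccination draw at Visit 1, which section 2.2 says evaluates influenza-specific immunity at entry, and section 11.4 models change from baseline. Earlier priming is therefore measurable. This stands in part. However, the blood is taken only where it can be obtained, 2.2 describes detection of undocumented infection only for the season 2 draw, and no rule uses the Visit 1 sample to confirm that an infant is naive.

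Second, 2.2 restricts 1A to infants without previous infection or vaccination. This also stands in part: the restriction can remove only known infection, and 5.1/5.2 do not carry it.

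Third, the calendar is assumed. That is correct, and the percentages are conditional on it.

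Stronger readings are tempting:

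- A reader might infer that the arms differ in actual prior exposure by design. The arithmetic shows opportunity only, often for part of a season.
- A reader might infer that the 1A v 1B contrast will shrink or reverse. The documents give no infant attack rate, effect size or standard deviation, and 11.2 says variability is unknown, so no such effect can be computed.
- A reader might conclude that cohort 1 needs a birth-date bound. With a 31 March season end, such a bound leaves 0/8/25/42% of the 1A band for mid-September to mid-December doses; with 30 April it leaves 0/0/8/25%. That nearly removes fall recruitment.

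**Conclusion.** The age band in 5.1 does not deliver the property that 2.2 claims for 1A. With fall dosing and a December-March season, about 58-100% of 1A infants were alive during part of the previous season, against about 6-39% of 1B infants (17-50% with a season end of 30 April). The direction of the difference holds in the averages under all four season windows. It rests on uniform ages, fall first doses and mid-winter infection; that most 1B infants are in their first season does not hold for early December infection with a long season. What follows is an unequal opportunity for unrecognised earlier infection, which limits how firmly the trial can call the 1A response primary. It does not establish that any 1A infant was exposed or that the comparison is biased by a known amount.

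**What to change.** - Correct the first-season statement in 2.2 so that it claims only what the age band secures.
- Carry the 2.2 condition of no previous influenza infection or vaccination into 5.1 or 5.2 for 1A.
- Derive a yes/no flag, alive during the previous season, from date of birth, with the season's start and end dates fixed before analysis.
- Add a sensitivity analysis of 1A v 1B that reports results by the flag and repeats the comparison without infants whose Visit 1 pre-vaccination sample, where obtained, shows influenza-specific CD4 reactivity. Define reactivity in advance against the negative controls in 8.2.2.
- Keep the age band and do not impose a birth-date bound.

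No new visits or samples are needed. The costs are analytic. First-season infants in 1A may be few: about 2 of 20 for mid-October dosing (8% of 20) and about 8 of 20 for mid-December (42% of 20), with a 31 March season end. Using the flag as a covariate widens the interval (standard error up about 5-55% in the pairings above), so reporting by flag as a sensitivity analysis is preferable to changing the main model. The reactivity exclusion works only in 1A, because the first 1B sample is taken during illness or skipped, and only in infants with a Visit 1 sample. It should be read as a check on the main result and not as a replacement for it.

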5.2 Exclusion Criteria

- Immunosuppression as a result of an underlying illness or condition (including HIV or a primary immunodeficiency syndrome)
- Active neoplastic disease
- Use of potentially immunosuppressive medications currently or within the past year (including chemotherapeutic agents) or chronic (>2 weeks) use of oral corticosteroid therapy
- A diagnosis of asthma requiring chronic inhaled corticosteroid use
- Participation in any clinical research study evaluating an investigational drug or therapy that is inconsistent with current standard of care within two (2) months of enrollment in this study.
- Previous administration of influenza vaccine in the current influenza season **ONLY** for subjects in the vaccination arm (A) of the study (subjects presenting with acute influenza infection with vaccine failure will be eligible to enroll in the B cohorts).
- Receipt of immunoglobulin or another blood product within the year prior to study enrollment
- An acute illness within the previous 3 days or temperature >38°C on screening **EXCEPT** for participation in the natural infection (B) cohorts
- A contraindication to influenza vaccination EXCEPT infants between 3 and 5 months presenting with natural influenza infection whose only contraindication is their current age
- Anemia in the previous 6 months (children on iron supplementation with no documentation of abnormal hemoglobin and/or hematocrit for >6 months will be allowed to participate in the study)
- Recent (within 120 days) hospitalization, excluding hospitalization for delivery or subjects enrolled in the acute cohort who have been hospitalized for influenza-related reasons
- Any medical history or other condition that the study PI feels may have a more than a minimal impact on the immune response or may impact the safety of the subject.

5.3 Handling of Withdrawals

If the child and parent/LAR are unwilling to participate further, then they may withdraw consent for study participation without penalty. Participants who withdraw, or are withdrawn or terminated from the study, or are lost to follow-up after receiving the assigned vaccine will not be replaced. Participants who consented to study participation in the vaccination cohorts but did

not receive the influenza vaccine will be replaced. These subjects will be considered as screen failures.

Criteria for withdrawal from the study will include

- Study participants may withdraw their consent for study participation at any time during the study without penalty
- The subject is unable to comply with study procedures or visits
- The principal investigator determines that it is in the best interest of the participant to discontinue participation
- The participant is lost to follow-up
- The study is terminated

Whether to exclude a previously enrolled subject if exclusion criteria are met at a visit following enrollment will be decided on a case by case basis (a subject may be allowed to continue in the study in the case of initiation of controller asthma medication, a hospitalization with an apparently full recovery, a single short oral steroid treatment course to treat reactive airway disease exacerbation, or in other instances where the PI decides that study continuation will not compromise either subject safety or the integrity of the data). If a subject has a temperature $>38.3^{\circ}\text{C}$ (101°F) at the time of a follow up visit, more than one episode of vomiting or diarrhea in the previous 24 hours, or symptoms of illness (respiratory or otherwise) that are interfering with activities of daily living (such as resulting in school or daycare absence) the study visit will be rescheduled or cancelled until the child recovers.

